1.3 SCHEDULE OF ACTIVITIES (SOA)

Procedures	Screening	Baseline	Ketamine Infusions	24 hour Follow-Up Visit	Assessment of Response to Ketamine	WET Sessions	Weekly Assessment Until 12 weeks	Monthly Assessment Until Loss-of-Response
	Day - 28 to 0	Visit 1a, Day 1	Visit 1a-9; Days 1, 3, 5, 8, 11, 12	Visit 1b, Day 2	Visit 5, Day 9	Visit 6-12, Days 10, 12, 16, 18, 22	Visits 10, 13-23, Days 12, 19, 26...	Visits 23-26, Days 33...
Informed consent	x							
Demographics	x							
Medical history	x							
SCID-5	x							
CAPS-5	x	x			x		x	x
MADRS	x	x			x		x	x
WTAR	x							
MoCA	x							
IES-R		x	x	x	x			
QIDS-SR		x	x	x	x			
PCL-5	x	x			x		x	x
MOS-5		x					x ¹	
CES		x					x ¹	
PACT		x					x ¹	
CTQ	x							
TLEQ	x							
SDS	x	x		x	x		x	x
HMS			x ²					
PIQ			x ²					
C-SSRS	x	x			x		x	x
CADSS		x	x					
BPRS		x	x					
YMRS		x	x					
Extinction Learning Task	x				x			
CGI	x	x	x	x	x		x	x
Concomitant medication review	x	x	x	x	x		x	x
PRISE	x	x	x	x	x		x	x

Adverse event review and evaluation	x	x	x	x	x	x	x	x
Physical exam (including height and weight)	x							
Vital signs	x		x					
Weight	x		x					
EKG	x							
Routine labs	x							
Plasma ketamine and norketamine levels			x ³					
Urine pregnancy test	x		x					
Urine drug screen (UTOX)	x		x					
Ketamine infusion (0.5 mg/kg)			x					
Written Exposure Therapy (WET)						x		
Complete Case Report Forms (CRFs)	x	x	x	x	x	x	x	x

¹Visit 14 and 23 only

²only at Infusions 1 and 2

³only at Infusion 1

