a. Screening Procedures (see 3.1 Schedule of Activities): Individuals will undergo informed consent procedures and study screening at the clinical site. If the COVID-19 pandemic remains a concern, these procedures will be conducted remotely, via a HIPAA-compliant telehealth platform (e.g., VSee, Doximity, HIPAA-Zoom). After signing the informed consent form, participants will complete a structured diagnostic interview with the SCID-5,⁵¹ the CAPS-5 to determine PTSD symptom severity,⁵⁰ the MADRS to determine depressive symptoms severity,^{52,53} the Wechsler Test of Adult Reading (WTAR),⁵⁴ and the Montreal Cognitive Assessment test (MoCA).⁵⁵ Please see **3.1 Schedule of Activities** for a complete list of scales to be completed by study participants at screening. All subjects will complete forms related to demographics, medical history, concomitant medications and treatment, and self-report measures including the Childhood Trauma Questionnaire (CTQ),⁵⁶ Traumatic Life Events Questionnaire (TLEQ),⁵⁷ PTSD Checklist for DSM-5 (PCL-5),⁵⁸ and Sheehan Disability Scale (SDS).⁵⁹ Participants will also undergo a medical evaluation, including medical history; physical examination by a nurse practitioner; documentation of height, weight and vital signs; comprehensive blood tests; and urinalysis, urine toxicology screen, and urine pregnancy test (in women of childbearing potential). After reviewing all information, the PI or other study psychiatrist will meet with each patient to review their psychiatric and medical history, and current medications and treatment, answer any questions the patient might have,

administer the Columbia Suicide Severity Rating Scale (C-SSRS)⁶⁰ and the CGI-S,⁶¹ document contraceptive use, and verify patient eligibility for the study. If a participant is taking any exclusionary psychotropic medication listed in the exclusion criteria, the prescribing psychiatrist or other prescribing physician must taper the participant off the medication, in consultation with the study PI or other study psychiatrist, if it is determined that the medication is of no clinical benefit to the individual.

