f. Online Extinction Learning Task (see **Figure 7** : The computerized task, administered online, consists of three phases: an initial aversive conditioning phase (in context A), extinction learning phase (in context A), and further extinction learning (in novel context B) (see **Figure 6**). Importantly, the conditioned stimulus (CS) associated with the aversive loss outcome (US), the CS+, is only partially reinforced ($P(US|CS+)=1/3$), and the transition to extinction ($P(US|CS+)=0$) is unsignaled. This design maximizes uncertainty about whether CS+ trials during extinction should be grouped with unreinforced conditioning phase CS+ trials, implying a common cause is responsible for both kinds of observations, or instead that the change in contingencies indicates it is likely that a new cause is active in the environment. The predictive measure generated from this task for Aim 2 analyses is the *difference in discrimination between CS+ and CS-* across the first six blocks of the task. Further, loss expectancy ratings data from each trial of the online extinction task will be analyzed via a computational model of latent cause inference developed by Gershman, Niv, and colleagues^{75,76} (see **Data Analysis Strategy**). There are *two versions of the task* (see **Figure 7** note): one version will be administered prior to any ketamine infusions, and the second version

after completion of the first four infusions. We will examine whether ketamine-induced improvement in extinction learning is associated with improvement in PTSD symptoms from baseline to 12 weeks from start of WET.

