For Aim 2, extinction learning will be measured twice, with two versions of the online Extinction Learning Task: (1) before the first ketamine infusion and (2) after completion of four ketamine infusions (pre-WET). Extinction learning will be defined as the difference in discrimination between the aversively conditioned (CS+) and safe (CS-) stimuli on the first six blocks of this task. Ketamine-induced change in extinction learning will be evaluated as a predictor PTSD symptom improvement from baseline to 12 weeks from the start of WET. A recently developed computational model^{75,76} will be employed to determine whether differences in discrimination between CS+ and CS- are related to differential inferences about the causal structure of the task during learning (i.e., participants' belief that one vs. multiple underlying causes explain observations during progression through the task).⁴⁸

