5.4 SCREEN FAILURES

Screen failures are defined as participants who consent to participate in the clinical trial but are not subsequently assigned to the study intervention or entered in the study. A minimal set of screen failure information is required to ensure transparent reporting of screen failure participants, to meet the Consolidated Standards of Reporting Trials (CONSORT) publishing requirements and to respond to queries from regulatory authorities. Minimal information includes demography, screen failure details, eligibility criteria, and any serious adverse event (SAE).

Individuals who do not meet the criteria for participation in this trial (screen failure) because of an exclusionary concomitant medication, or a recent change in medications or psychotherapy may be rescreened. Rescreened participants should be assigned the same participant number as for the initial screening.

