extinction learning (in novel context B) (see Figure 7). Importantly, the conditioned stimulus (CS) associated with the aversive loss outcome (US), the CS+, is only partially reinforced ($P(US|CS+)=1/3$), and the transition to extinction ($P(US|CS+)=0$) is unsignaled. This design maximizes uncertainty about whether CS+ trials during extinction should be grouped with unreinforced conditioning phase CS+ trials, implying a common cause is responsible for both kinds of observations, or instead that the change in contingencies indicates it is likely that a new cause is active in the environment. The predictive measure generated from this task for Aim 2 analyses (PTSD symptom change between baseline and 12 weeks from the start of WET) is the difference in discrimination between CS+ and CS- across the first six blocks of the task.

Further, loss expectancy ratings data from each trial of the online extinction task will be analyzed via a computational model of latent cause inference developed by Gershman, Niv, and colleagues^{75,76} (see Data Analysis Strategy). There are two versions of the task (see description in Figure 7 note): one version will be administered prior to any ketamine infusions, and the second version after completion of the first four infusions. We will examine whether improvement in extinction learning from baseline to completion of four initial ketamine infusions (prior to starting WET) is associated with PTSD symptom improvement from baseline to 12 weeks from the start of WET.

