The relationship between depressive symptoms and PTSD will be explored to assess whether worsening depressive symptoms correlate with worsening PTSD symptoms and whether there is any evidence that the worsening of one precedes the other. Scale scores of both measures will be plotted over time together to evaluate trends descriptively. Fixed and mixed effects regression models will also be explored to estimate effects and 95% confidence intervals.

- Finally, additional analyses might explore differences with a historical comparison group from our published repeated IV ketamine study for PTSD (Feder et al 2021).

Aim 2 (Exploratory): To evaluate whether ketamine-induced change in extinction learning predicts maintenance of ketamine response over time. We will use regression models to evaluate whether ketamine-induced change in extinction learning [improvement in extinction learning between two time points: (1) before infusions and (2) after four infusions (prior to starting WET), measured with the computerized online Extinction Learning Task, is associated with change in CAPS-5 at 12 weeks after the start of WET. A univariable model of ketamine-induced change on the extinction learning measure [discrimination between aversively conditioned (CS+) and safe (CS-) stimuli over the first six blocks of the task] and changes in CAPS-5 score will be examined. Beta coefficients and 95% confidence intervals will be reported. A significant association between greater ketamine-induced improvement in extinction learning and improvement in CAPS-5 scores will be considered supportive of Hypothesis 2.

Computational analyses: Loss expectancy ratings data from each trial of the online extinction task will be analyzed via a computational model of latent cause inference developed by Gershman, Niv, and colleagues.^{75,76} Importantly, this model has previously been shown to be able to explain individual differences in failure of extinction learning in both healthy volunteers and trauma-exposed individuals

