10.1.1.2 CONSENT PROCEDURES AND DOCUMENTATION

After completing the screening process at DAC through protocol STUDY-10-00606, potentially eligible participants will be invited to participate in a screening visit for this protocol. Informed consent may be obtained in person or remotely, using a HIPAA-compliant telehealth platform(e.g., VSee, Doximity, HIPAA-Zoom) and the electronic consent survey housed on REDCap. As the proposed study involves ketamine infusions, the informed consent will be obtained by either the PI or one of the study-affiliated psychiatrists. Consent may be obtained by a clinical research coordinator prior to administering clinical rating scales, self-report scales, the extinction learning task, and/or the medical clearance assessment. In this case, the PI or study-affiliated psychiatrist will re-review the consent form with the participant and will co-sign the form prior to the participant beginning the first study intervention (ketamine infusions). Potential participants will be informed about possible alternatives to participating in the study. A release of information will be obtained for review of any available historical and clinical data. Authorization is also obtained from each subject in the consent document, permitting the research team to use, create, or disclose the subject's PHI for research purposes. The nature of the project, procedures, relative risks and benefits, and alternatives to participation in the project will be discussed with the individual. The individual will be given ample opportunity to ask any questions they might have. Following this discussion, the individual will be given a physical or electronic copy of the consent form to review at their leisure, and any remaining questions will be answered. If the individual remains interested in the project, written or electronic informed consent is obtained, and medical and psychiatric screening procedures are undertaken to confirm eligibility. If the individual decides not to participate in this study, a staff member provides reasonable and timely assistance in obtaining an alternative referral, if so desired. The decision not to participate does not affect eligibility to participate in future studies, to receive treatment at Mount Sinai or at any program serving PTSD populations, or to receive treatment on a private basis. Subjects will be also be given the opportunity to withdraw from the study at any point. The consent process also includes documentation of permission to obtain previous medical records, including contact with previous physicians, pharmacies, and family members.

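### The pre-ketamine Extinction Learning Task is scheduled only at screening (Day -28 to 0), so the interval behind the Aim 2 change score can run from 9 to 37 days, up to 29 of them before any ketamine

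*Combined protocol and SAP*

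**What the plan says.** Section 1.3 marks "Extinction Learning Task" in two columns: Screening, which spans Day -28 to 0, and the assessment of response to ketamine on Day 9. The Baseline column (Visit 1a, Day 1) has no mark. CAPS-5, MADRS, PCL-5 and SDS are marked at both Screening and Baseline.

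The text is looser on timing. Section 4.1(f) says "one version will be administered prior to any ketamine infusions, and the second version" follows the first four infusions. Section 4.2 gives the two time points as "1) before the first ketamine infusion and (2) after completion of four ketamine infusions (pre-WET", with no day or window. Section 8.1 speaks of "improvement in extinction learning from baseline to completion of four initial ketamine infusions", and the justification column in section 3 also compares with baseline. Section 9.4.3 enters the difference between the two scores as ketamine-induced change in a univariable regression on CAPS-5 change, and says a significant association would support Hypothesis 2.

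Three further provisions bear on what can happen during screening:

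- Section 4.1(a): for a participant on an exclusionary psychotropic, the prescriber "must taper the participant off the medication, in consultation with the study PI or other study psychiatrist", provided the drug is judged to bring no benefit.
- Section 5.4: people who fail screening "because of an exclusionary concomitant medication, or a recent change in medications or psychotherapy may be rescreened".
- Section 10.1.1.2: a coordinator may take consent "prior to administering clinical rating scales, self-report scales, the extinction learning task, and/or the medical clearance assessment".

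No section states where the task falls relative to a taper, or whether it is repeated at rescreening.

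**The concern.** The Aim 2 predictor is a difference of two scores, so whatever happens between the two sittings enters it. If the first sitting can be four weeks before infusion 1 for one participant and the day before for another, the change score covers a different untreated stretch in each. For a participant who tapers a drug or is rescreened in that stretch, it may also cover a medication change. The plan attributes the whole difference to ketamine, with no control arm (section 6.3) and no model term for interval or medication change (section 9.4.3).

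The plan re-measures its main symptom scales on Day 1 but not this predictor. The CAPS-5 change it is meant to explain starts at baseline, so predictor and outcome also start from different points. At stake is the interpretation of Aim 2: what a slope fitted to at most 15 participants (section 9.2) can be said to show.

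**Working it through.** **The plan's own figure.** Section 9.2 gives one precision figure, for the primary endpoint: a 95% half-width of 0.5 SD at N = 15. With the SD treated as known, 1.96/√15 = 0.506 SD, which reproduces it. The plan gives no figure for Aim 2, and the point here does not depend on this one.

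**Timing.** Inputs from section 1.3: first task on day d, with d between -28 and 0; infusion 1 on Day 1; second task on Day 9. Days before ketamine = 1 - d. Gap between tasks = 9 - d. Share of the gap before ketamine = (1 - d)/(9 - d).

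| First task on | Days before infusion 1 | Gap to second task | Share before ketamine |
|---|---|---|---|
| Day -28 | 29 | 37 | 29/37 = 78% |
| Day -14 | 15 | 23 | 15/23 = 65% |
| Day 0 | 1 | 9 | 1/9 = 11% |
| Day 1, pre-infusion | 0 | 8 | 0% |

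This counts Day 0, as the schedule does; otherwise the extreme is 28 and 36 days. Under the current schedule the gap can differ between two participants by 37 - 9 = 28 days. If the first task fell on Day -2 to Day 1 before infusion, the gap would be 8 to 11 days, a spread of 3.

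**Can a taper fall between the tasks?** Exclusion 18 (section 5.2) asks for two weeks off the named drugs before study start. If study start means infusion 1, two weeks fit inside a 28-day window, so the sequence task, taper, infusion is possible. It is not prescribed.

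**What noise would do (illustration, assumed inputs).** Let s be the share of change-score variance unrelated both to ketamine and to outcome. The expected correlation is then r·√(1 - s). At N = 15, two-sided p < 0.05 needs |r| ≥ 2.160/√(13 + 2.160²) = 0.514. Simulated power (40,000 bivariate normal samples per cell):

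| True r | s = 0 | s = 10% | s = 25% | s = 50% |
|---|---|---|---|---|
| 0.5 | 50% | 45% | 38% | 26% |
| 0.6 | 70% | 64% | 54% | 36% |
| 0.7 | 88% | 82% | 71% | 49% |

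For r = 0.6 the expected observed correlations are 0.60, 0.57, 0.52 and 0.42. The documents supply neither r nor s, so the table shows direction and sensitivity only. It does not estimate the effect in this trial.

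**The case against.** The strongest reply is that a screening score does precede every infusion, which is all that sections 4.1(f), 4.2 and 9.4.3 ask, and that a site testing on Day 0, or after a taper, complies fully. That is correct. The schedule permits the long gap without imposing it. But it is the only place that gives days, it separates Screening from Baseline, and it leaves the gap uncontrolled.

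Several stronger readings are tempting, and the documents do not support them:

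- *That the first task is given before tapers or rescreening.* No section fixes that order. Section 10.1.1.2 concerns who may take consent, and its and/or list sets no sequence. Candidates first pass screening under a separate protocol, so excluded drugs may be found earlier. Study start in exclusion 18 is undefined, while exclusion 7 refers to the first infusion day. Other psychotropics must be stable for three months. The number who would taper is not given and could be zero.
- *That 78% of the change score is contaminated.* That is a worst-case share of calendar days. It says nothing about the share of variance or the size of any bias.
- *That repeat exposure results from the screening timing.* Any two-test design has it. The two versions share one structure (section 8.1, Figure 7 note), so everyone meets the unsignaled switch again on Day 9, whenever the first task is done. Only a rescreened participant who repeated version 1 would have extra exposure.
- *That an association could be manufactured.* Noise unrelated to outcome weakens an association. Creating one needs screening events correlated with 12-week CAPS-5 change; this is possible, but nothing in the documents shows it.

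It is also fair that Day 1 is crowded. Participants are fasting (section 5.3), and the visit already holds a CAPS-5 of about 40 minutes and the first infusion. This argues for a short window in place of a strict Day 1 requirement. Finally, without a control arm even Day 1 testing would not isolate ketamine. That stands, and it limits what the fix can achieve.

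**Conclusion.** The point holds as a scheduling weakness in an exploratory aim. The first task is tied to a four-week screening window while the predictor is described as change from baseline and attributed to ketamine. The gap can vary from 9 to 37 days, with 1 to 29 days before treatment, against 8 days for everyone if tested on Day 1. These figures rest only on the schedule's day numbers, counting Day 0.

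The likely consequence is extra noise, and possibly some bias, in a predictor with at most 15 points. The size cannot be computed, because the documents give no test-retest drift for the task, no distribution of screening intervals and no number of tapers or rescreenings. The primary endpoint and its analysis are not touched. This is a cheap improvement rather than an error that undermines the trial, but a pre-infusion score that was not collected cannot be recovered once a participant has been treated.

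**What to change.** - In section 1.3, move the first task mark from the Screening window to a short fixed window before infusion 1, after eligibility is confirmed and any taper or rescreening is complete. The last 3 days would do (an assumed figure); Day 1 before the infusion is also acceptable.
- State that each participant takes version 1 once only.
- Record the date of each task and report the interval between them.
- Bring sections 4.1(f), 4.2, 8.1 and 10.1.1.2 into line with the new timing.
- In section 9.4.3, report the predictor as pre-to-post change in extinction learning, because practice and version effects remain after the move and there is no control arm.

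The cost is one schedule mark, a few sentences and one more task close to infusion 1, which can be done online at home. For anyone already tested under the current schedule, the interval and any medication change between the two tasks can still be recorded and shown alongside the Aim 2 result.

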2 INTRODUCTION

2.1 STUDY RATIONALE

Posttraumatic stress disorder (PTSD) is a chronic and disabling condition. Trauma-focused psychotherapies for PTSD have the strongest evidence base. Access to these specialized forms of therapy, however, is often limited by geographic, economic, and time-commitment barriers, as well as need for extensive therapist training. Additionally, 25-40% of patients drop out of treatment prematurely. There is thus a strong need to develop more efficacious and scalable treatments for PTSD.

Recent evidence from our research group showed efficacy of repeated intravenous (IV) infusions of ketamine at sub-anesthetic doses (0.5 mg/kg) in rapidly improving PTSD symptoms in patients with chronic PTSD, as well as co-morbid depressive symptoms. However, these effects are time-limited, with loss of initial response to ketamine within 2 to 4 weeks following a course of six infusions. Additionally, results from pre-clinical studies suggest that ketamine administration might facilitate fear extinction learning.

Building on these findings, the current project will evaluate the efficacy of **adding Written Exposure Therapy (WET) to a course of repeated IV ketamine infusions** in improving PTSD symptoms from pre-

infusion baseline to 12 weeks from the start of WET, in patients with chronic PTSD. WET is a brief, 5-session evidence-based written trauma-focused therapy without in-between-session assignments, with demonstrated efficacy and low dropout rates in patients with PTSD. WET will be administered to participants starting after they receive four initial ketamine infusions; the first WET sessions will be interleaved with two additional ketamine infusions to take advantage of a window of increased neuroplasticity potentially induced by repeated ketamine infusions. WET be administered on different days as the ketamine infusions.

